 - Carotid endarterectomy, carotid stenting, or more than 70% stenosis in a carotid artery determined by carotid ultrasound or angiogram (Note: If stenosis assessed by carotid ultrasound is reported as range between 60%-79%, patient may qualify only if internal carotid artery peak systolic velocity is >230 cm/sec), occurring greater than 90 days prior to screening, **or**
- b. High risk for a CVD event (ie, high-risk primary prevention)
 - Reynolds Risk score >30% or a SCORE Risk score >7.5% over 10 years (see Appendix 3 and Appendix 4 for additional details), **or**
 - Coronary artery calcium score >400 Agatston units (AU) at any time in the past, **or**
 - Patients with type 1 or type 2 diabetes, aged >65 years (women) or >60 years (men).

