7.4. Diabetes Related Definitions

7.4.1. Baseline Glycemic Status

Analyses of diabetes and related biomarkers are conducted with specific subsets of study population based on the baseline glycemic status defined in Table 1.

- For efficacy analyses of new-onset type 2 diabetes (conducted in the study population with No Diabetes at baseline), and related biomarkers HbA1c and fasting glucose, the FAS (or PPS for sensitivity analyses) is used with subpopulations defined according to the baseline glycemic status.
- For safety analyses of AESIs of *new-onset diabetes* (conducted in the study population with No Diabetes at baseline), and *worsening hyperglycemia* (Diabetes at baseline), and related safety laboratory measures including HbA1c and fasting glucose, the SAS is used with subpopulations defined according to the baseline glycemic status.

Table 1: Baseline Glycemic Status

Status	Definition
Diabetes	Meeting 1 or more of the following criteria at baseline captured by information recorded prior to Day 1: 
 • Medical history or adverse events indicating diabetes as defined in the Diabetes Committee Charter (attached as Appendix 8) • Prior glucose-lowering medication as defined by the Diabetes Committee Charter (attached as Appendix 8) • HbA_{1C} measurement $\geq 6.5\%$ • Two or more measurements of fasting glucose ≥ 126 mg/dL (7.0 mmol/L)
Inadequately Controlled (IC) Diabetes	With Diabetes and a HbA _{1C} of 7% or greater at baseline.
No Diabetes	Not meeting any of the criteria for Diabetes at baseline.
Prediabetes	No Diabetes at baseline, and with: 
 • HbA_{1C} measurement of $\geq 5.7\%$ and $< 6.5\%$, OR • 1 or more measurements of fasting glucose ≥ 100 mg/dL (5.6 mmol/L), but not more than 1 value of fasting glucose ≥ 126 mg/dL (7.0 mmol/L).
Normoglycemia	No Diabetes, and not meeting the criteria for Prediabetes at baseline.

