11. DEMOGRAPHIC AND BASELINE CHARACTERISTICS

Demographic data and other baseline characteristics will be summarized by treatment group for the FAS, SAS and PPS. These data will also be provided for patients in the SAS with baseline ezetimibe use. No statistical testing will be carried out for demographic or other baseline characteristics.

The following demographic and other baseline characteristics will be summarized and listed for this study:

- Age (years)
- Age category (<65 years, ≥65 to <75 years, or ≥75 years)
- Sex (female vs male, at birth)
- Race (American Indian or Alaska Native, Asian, Black or African American, Native Hawaiian or Other Pacific Islander, White, and Other)
- Ethnicity (Hispanic or Latino vs Not Hispanic or Latino)
- Region (defined in Section 7.5.1)
- Weight (kg)
- Height (cm)
- Body mass index (BMI) (kg/m^2) = $\text{weight (kg)}/\text{height (m)}^2$
- BMI category (<25 kg/m^2 , 25 to <30 kg/m^2 , or ≥30 kg/m^2).
- Baseline vital signs (systolic blood pressure, diastolic blood pressure, and heart rate)
- Baseline key laboratory Results (LDL-C, hs-CRP, Non-HDL-C, TC, HDL-C, and TG) (LDL-C results are presented in both conventional and standardized units, the others will be in conventional units only)
- Baseline LDL-C category (<130 mg/dL, ≥130 mg/dL and <160 mg/dL, ≥160 mg/dL)
- Baseline hs-CRP category (<2 mg/L, ≥2 mg/L)
- Baseline CVD risk category (Section 7.5.3), for patients with documented CVD history (secondary prevention), the prior history of CAD, PAD or CeVD.
- History of diabetes mellitus (Yes vs No, as collected in the *Targeted Cardiovascular History/Risk Factors* CRF)
- Baseline glycemic status (Section 7.4)
- History of hypertension (Yes vs No, Section 7.5.2)
- Alcohol consumption (Non-drinker, Former Drinker, or Current drinker)
- Tobacco use (Never used, Former user, or Current user)
- Baseline background lipid-modifying therapy (LMT) (Statin use including statin only or Statin + other LMT, other LMT without statin, or none, see also Section 7.6.1)

- Baseline statin intensity (none, very low, low, moderate, and high, see [Section 7.6.2](#) and [Appendix 5](#))
- Baseline ezetimibe use (Yes vs No)
- Statin intolerance criteria as collected on the *Statin Intolerance Criteria Compliance* CRF [REDACTED]
- Baseline estimated glomerular filtration rate (eGFR) category (≥ 90 mL/min/1.73m²; 60 to <90 mL/min/1.73m²; 30 to <60 mL/min/1.73m²; or <30 mL/min/1.73m²)

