12. MEDICAL AND SURGICAL HISTORY

General medical and surgical history information will be presented by Medical Dictionary for Regulatory Activities (MedDRA) SOC and PT for the FAS. Medical history conditions are those conditions that started prior to screening and collected on the *Medical History* CRF.

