16.1.2. Adverse Events of Special Interest

 AESIs will be identified by specified MedDRA PTs, or the related laboratory criteria if applicable. See [Appendix 7](#) for the list of AESIs and their definitions. These events will be summarized by AESI category, laboratory criteria met (if applicable), and PTs.

The NODM AESI is applicable only for patients with baseline glycemic status ([Section 7.4](#)) of No Diabetes at baseline. As an AESI vs. an efficacy endpoint, NODM includes a broader definition of NODM with patients who meet one of the following conditions:

- patients with verified NODM as determined by the DC ([Section 7.4.3](#)), or
- patients who initiated a diabetes medication after first dose of IMP ([Appendix 8](#)), or
- patients meeting the laboratory criteria for NODM as in [Appendix 7](#), or
- patients with selected AE preferred terms (see list of preferred terms for ‘NODM’ in [Appendix 7](#)).

Worsening Hyperglycemia AESI is applicable to patients with baseline glycemic status of Diabetes based on adverse event preferred terms as described in [Appendix 7](#).

See [Appendix 7](#) for the list of AESIs and their definitions. AESIs will be identified by specified MedDRA PTs, and/or the related laboratory criteria if applicable. These events will be summarized by treatment group, and by AESI category, laboratory criteria met, and PTs.

Malignancy AESI will be summarized by Standardised MedDRA Queries (SMQs) and PTs as described in [Appendix 7](#).

Tendon rupture will be summarized for events that are positively adjudicated according to the TRAC Charter. All potential tendon ruptures that were reviewed by the TRAC will be presented in a listing.

For AEs considered to be muscle related by the Investigator, additional information is collected on the *Muscle Related Adverse Event Complementary* CRF including the primary cause, locations, and whether the AE is unilateral or bilateral.

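### The baseline diabetes definition in SAP Table 1 leaves out the Yes/No diabetes history item on the targeted cardiovascular CRF, so a small group of recorded diabetics can enter the new-onset diabetes analyses

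*SAP*

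**What the plan says.** SAP 7.4.1, Table 1, assigns Diabetes status on "Meeting 1 or more of the following criteria at baseline captured by information recorded prior to Day 1". There are four criteria:

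- for history, it takes "Medical history or adverse events indicating diabetes as defined in the Diabetes Committee Charter (attached as Appendix 8";
- for drug treatment, it takes "Prior glucose-lowering medication as defined by the Diabetes Committee Charter (attached as Appendix 8";
- for HbA1c, the threshold is 6.5% or more;
- for glucose, it asks for "Two or more measurements of fasting glucose", each reaching 126 mg/dL.

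No Diabetes is the absence of all four. Prediabetes and Normoglycemia are carved out of No Diabetes. Appendix 8 is a list of preferred terms and ATC drug classes; no CRF tick-box item appears in it.

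SAP 11 lists a separate baseline variable, "History of diabetes mellitus (Yes vs No, as collected in the" (the form named there is the targeted cardiovascular history CRF), next to baseline glycemic status. SAP 12 describes its own history summary this way: "Medical history conditions are those conditions that started prior to screening and collected on the" (the form named there is the Medical History CRF). Protocol 7.1, inclusion 7b, accepts as high risk "Patients with type 1 or type 2 diabetes, aged >65 years (women) or >60 years (men", so diabetes plus age is an entry route by itself.

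For efficacy, SAP 15.3.2 analyses only new-onset diabetes events verified by the Diabetes Committee, with Prediabetes as the primary subset. The AESI in SAP 16.1.2 is broader. Besides verified cases, it accepts "patients who initiated a diabetes medication after first dose of IMP", laboratory criteria, or selected adverse event terms.

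**The concern.** The trial holds diabetes history in two places and Table 1 reads one of them. SAP 7.5.3 already uses the targeted form to classify cardiovascular risk, so the form is available to the analysis. No visible section reconciles the two sources.

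Table 1 fixes who is at risk of new-onset diabetes. If a patient with recorded diabetes is placed in No Diabetes, two things follow on the safety side. Starting a drug or crossing a laboratory threshold counts as new-onset disease without committee review. In addition, a worsening of existing diabetes cannot enter the worsening hyperglycemia AESI, because that category is limited to patients with baseline Diabetes. Dilution toward 1 is not a conservative error in a safety comparison, since it would understate a real excess. The same subsets also carry the efficacy endpoint, the HbA1c and glucose analyses and the exploratory glycemic-status subgroups for MACE.

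**Working it through.** **Step 1. Who is missed.** Any one of the four criteria is enough, so a known diabetic is missed only if all of these hold:

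- no Medical History or adverse event term on the Appendix 8 list;
- no recorded prior glucose-lowering drug (Protocol 8.2 collects nonstatin drugs only from 3 months before screening);
- HbA1c below 6.5%;
- fewer than two fasting glucose values at or above 126 mg/dL.

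This is chiefly an untreated, well-controlled patient whose diabetes was ticked on the targeted form and not repeated as medical history. A patient whose history page shows only a complication missing from the printed Appendix 8 list, such as diabetic neuropathy or retinopathy, is in the same position. With HbA1c of at least 5.7% or one fasting glucose of at least 100 mg/dL, the patient becomes Prediabetes.

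**Step 2. Inputs for size.** The plan states no figure on this point, so there is nothing to reproduce. All of the following are assumptions:

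- N = 7,000 to 8,400 No Diabetes patients (50% to 60% of 14,000);
- m = 0.5% to 2% of them recorded only on the targeted form, that is 7,000 × 0.005 = 35 to 8,400 × 0.02 = 168 patients;
- r0 = 3% to 5% per year true new-onset rate;
- r1 = 20% to 40% per year of missed diabetics meeting an AESI criterion;
- 3.5 years of follow-up.

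**Step 3. False AESI events**, N × m × (1 − exp(−3.5 r1)):

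- low: 35 × (1 − exp(−0.7)) = 35 × 0.5034 = 17.6;
- high: 168 × (1 − exp(−1.4)) = 168 × 0.7534 = 126.6.

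**Step 4. Share of all new-onset AESI events**, with true events taken at rate r0 in the remaining 1 − m (N cancels):

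- low (m = 0.005, r1 = 0.2, r0 = 0.05): 0.00252 / (0.00252 + 0.995 × 0.1605) = 1.6%;
- high (m = 0.02, r1 = 0.4, r0 = 0.03): 0.01507 / (0.01507 + 0.98 × 0.0997) = 13.4%.

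**Step 5. Dilution.** Take a hazard ratio of 0.85 in the truly at-risk patients and 1 in the missed diabetics. If f is the share of placebo-arm events that are false, the observed ratio is (1 − f) × true ratio + f. The 3.5-year risk ratio without misclassification is 0.857 (r0 = 0.03) or 0.861 (r0 = 0.05).

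- f = 1.6%: 0.861 becomes 0.863, a shift of 0.002.
- f = 13.4%: 0.857 becomes 0.876, a shift of 0.019.

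Over the whole grid the observed risk ratio runs from 0.860 to 0.876. The same formula applied to the hazard ratio as an approximation gives, for f = 1%, 2%, 5% and 10%, 0.852, 0.853, 0.858 and 0.865. A harmful ratio of 1.20 with f = 10% would read (0.90 × 1.20) + 0.10 = 1.18. A true ratio of 1 does not move.

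**Step 6. Efficacy endpoint.** If the committee verifies such an event, it is a false event and Step 5 applies. If the committee rejects it, the patient stays in the risk set without a countable event. Observed incidence is then multiplied by 1 − m: with r0 = 0.03 and m = 0.02, 0.98 × 9.97% = 9.77%. The risk ratio is unchanged, because both arms are scaled equally.

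**The case against.** The strongest reply is that the gap may be empty. The CRFs, completion guidelines and Diabetes Committee charter are not in the documents. Protocol 11.3 has sites record diabetes and related diagnoses as medical history or adverse events, and Protocol 12.1.1 singles out diabetes for careful history taking. A discordant patient needs a site that did otherwise. This stands, and it limits the size of the problem. It does not supply a rule for a patient whose two records disagree.

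It is also fair to say that Table 1 is in places wider than Protocol 15.4: adverse event terms count, and a listed drug is enough without committee confirmation. In addition, SAP 12 describes a summary table and does not by itself define the Table 1 criterion. The point rests on the Appendix 8 term list, so it survives without SAP 12.

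A reader might infer that known diabetics will generally be counted as efficacy events and that incidence is inflated throughout. The documents do not support that. Only verified events count, the committee works from eCRF and laboratory data (Protocol 11.3) and may well see the targeted form, and a rejected event lowers incidence. A reader might also take different counts for diabetes history and glycemic status in SAP 11 as a contradiction. They are different variables; glycemic status adds laboratory-only and drug-only cases, so the counts would differ after any fix.

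**Conclusion.** The gap is real in the text and minor in consequence. Table 1 disregards a diabetes history item that the trial collects, and a narrowly defined patient can therefore be treated as free of diabetes at baseline. How many such patients exist cannot be learned from the documents. Every input to the range of about 18 to 127 false AESI events is assumed, and the AESI laboratory criteria (SAP Appendix 7) are not available to check the assumed event rate.

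The misclassification arises before randomization and should be balanced, so the expected result is mild dilution of the new-onset AESI and some misplacement between AESI categories. SAP 16 plans no statistical comparison of safety data unless specified. Time to new-onset diabetes lies outside the testing hierarchy (SAP 8.3), and its p-value is nominal. The MACE glycemic subgroups are exploratory. Nothing here reaches the primary MACE result.

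**What to change.** Before unblinding, while the analysis sets are still open (SAP 6):

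1. Cross-tabulate the targeted-form item = Yes, and entry under 7b by diabetes where the database identifies it, against Table 1 status.
2. Send patients for whom this is the only evidence of diabetes to the blinded Diabetes Committee. Protocol 15.4 gives a model in its handling of medication-only cases. SAP Table 1 does not carry that step over, so the SAP must state it.
3. Add committee-confirmed cases to the Diabetes row of Table 1, then derive No Diabetes, Prediabetes and Normoglycemia.

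At minimum, report the number of discordant patients by arm and run a sensitivity analysis of new-onset diabetes, both efficacy and AESI, without them.

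The cost is one line in Table 1, a blinded data check and some committee time on ticks that prove mistaken. The history item is already collected.

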7.4.2. Antidiabetic Medications

For this study, antidiabetic medications are defined based on approved medications that lower blood glucose (Appendix 8).

Baseline antidiabetic medications are defined for the FAS as those ongoing at the time of randomization.

Patients are considered to have had a *change in background antidiabetic medications* if they had any new antidiabetic medications that either started, stopped or had a dose change during the 12 weeks (84 days) prior to screening (Visit S1) to within 12 months (365 days) post randomization. These patients are excluded from a sensitivity analysis of Month 12 HbA_{1c} response.

7.4.3. NODM as an Efficacy Endpoint

For efficacy evaluation, NODM will be assessed in the subset of patients who did not have diabetes at baseline (No Diabetes), including those patients in the subsets of “prediabetes” and “normoglycemia”, but develop postbaseline new onset type 2 diabetes mellitus, defined by 1 or more of the following criteria according to the 2020 American Diabetes Association (ADA) guidelines (ADA, 2020):

1. Fasting plasma glucose ≥ 126 mg/dL (7.0 mmol/L). Fasting is defined as no caloric intake for at least 8 hours;* or

2. Two-hour post-prandial glucose ≥ 200 mg/dL (11.1 mmol/L) during an oral glucose tolerance test as defined in the ADA guidelines;* or
3. HbA_{1c} measurement $\geq 6.5\%$ (48 mmol/mol);* or
4. In a patient with classic symptoms of hyperglycemia or hyperglycemic crisis, a random plasma glucose ≥ 200 mg/dL (11.1 mmol/L).

*Note: In the absence of unequivocal hyperglycemia, diagnosis requires 2 abnormal test results from the same sample or in 2 separate test results.

The NODM events will be verified by the Diabetes Committee based on the [REDACTED] Diabetes Committee Charter.

7.5. Other Baseline Characteristics

7.5.1. Region

Study patients are grouped by the sites' location into the following regions (GHDx, 2022):

- North America: Canada and United States.
- Latin America: Argentina, Brazil, Chile, Colombia, and Mexico.
- Western Europe: Austria, Belgium, Denmark, Germany, Great Britain, Netherlands, and Spain.
- Central and Eastern Europe: Bulgaria, Croatia, Czech Republic, Estonia, Hungary, Latvia, Lithuania, Poland, Romania, Russia, Serbia, Slovakia, and Ukraine.
- Other: Australia, India, New Zealand, South Africa, and Turkey.

7.5.2. History of Hypertension

A patient is considered to have had a history of hypertension if any preferred terms of the medical history (including events recorded on the Adverse Event CRF that started prior to the Day 1) match the terms listed in Appendix 11.

7.5.3. Baseline CVD Risk Category

A patient is in the category of secondary prevention for cardiovascular diseases (CVD) if there was any documented CVD history as recorded on the *Targeted Cardiovascular History/Risk Factors* CRF, including coronary artery disease (CAD), symptomatic peripheral arterial disease (PAD), or cerebrovascular atherosclerotic disease (CeVD). Otherwise the patient is considered in the high-risk primary prevention category.

7.5.4. History of Chronic Kidney Disease

A patient is determined to have a history of chronic kidney disease (CKD) if the medical history (including events recorded on the Adverse Event CRF that started prior to Day 1) includes preferred term *chronic kidney disease*.

7.6. Lipid-Modifying Therapy (LMT)

7.6.1. Definition of LMT

For this study, lipid-modifying therapy (LMT) includes:

- Statins: all available prior history of and concomitant statin use are recorded in the “Prior and Concomitant Statin Therapy for Dyslipidemia” CRF.
- Commercial bempedoic acid:
 - Bempedoic Acid alone: preferred name is “BEMPEDOIC ACID”.
 - Bempedoic Acid and Ezetimibe FDCP (fixed dose combination product): the verbatim term contains both “BEMPEDOIC ACID” and “EZETIMIBE”, or the brand names “NUSTENDI” or “NEXLIZET”.
- Other LMTs taken within 3 months prior to screening and concomitantly are recorded using the standard “Prior and Concomitant Medication” CRF, and a medication is classified as LMT if the coded ATC Level 2 (ATC2) term is "LIPID MODIFYING AGENTS". The non-statins LMTs are further classified based on coded terms:
 - Selected Cholesterol Absorption Inhibitors (Ezetimibe): preferred name contains “EZETIMIBE”, or Bempedoic Acid and Ezetimibe FDCP as noted above.
 - PCSK-9 Inhibitors (PCSK9i): preferred name is one of “EVOLOCUMAB”, “ALIROCUMAB”, or if the verbatim term contains “INCLISIRAN” or “LEQVIO”.
 - Bile Acid Sequestrants: ATC Level 4 (ATC4) term is “BILE ACID SEQUESTRANTS”
 - Fibrates: ATC4 term is “FIBRATES”
 - Niacin Derivatives: ATC4 term is “NICOTINIC ACID AND DERIVATIVES”.
 - Other: all other LMTs. In addition, this group also includes preferred name of “MONASCUS PURPUREUS” (red yeast rice) regardless of the ATC2 term.

Note that brand names are used in some cases because the coding dictionary (Section 8.4) does not contain the appropriate preferred names.

7.6.2. Categorization of Statin Intensity

Statin intensity at any given time is categorized as high, moderate, low, or very low based on average daily dose of the statin taken at the time and the cutoffs defined in Appendix 5 , or none if not taking statin at the time. Designations of statin dose intensity were modeled after the 2018 ACC/AHA Guideline on the Management of Blood Cholesterol (ACC/AHA, 2019). The table was modified by creating a “very low dose” statin intensity category that reflected the allowed statin dosing intensities used as background therapy in the trial (Protocol Section 7.1 Inclusion Criteria #2) and recognizes the different dosing regimens that statin intolerant patients may sometimes follow (such as alternate day dosing). The average daily dose is derived from the

dose and frequency recorded on the statin therapy CRF, or if the frequency is “Other”, the daily dose entered by the site is used.

7.6.3. Baseline LMT

Baseline LMT is defined as any lipid-modifying agents that were ongoing at the time of randomization.

Baseline statin intensity is derived using the baseline statin with the highest intensity.

Baseline ezetimibe use is defined as the use of ezetimibe alone or in combinations that were ongoing at the time of randomization.

7.6.4. Cross-in LMT

For patients in the FAS, cross-in LMT is defined as either initiation of new non-statin LMT or an increase in statin intensity after randomization that meets at least one of the following criteria:

1. Any statin, regardless of the specific drug, started after randomization, with increased intensity if used at baseline, and continued for 90 days or more.
2. Non-statin oral prescription LMTs (Bile Acid Sequestrants, Fibrates, Niacin Derivatives, Ezetimibe, commercial Bempedoic Acid, commercial Bempedoic Acid and Ezetimibe FDCCP, as defined in Section 7.6.1) that were not used at baseline (same preferred name), started after randomization and continued for 90 days or more.
3. PCSK9i started after randomization, not used at baseline (for evolocumab), or with increased intensity if used at baseline (specifically, for alirocumab switching from 75 mg once every two weeks to 150 mg once every two weeks or 300 mg once every 4 weeks), and continued for 90 days or more if mAb (evolocumab or alirocumab); or ≥ 1 dose for siRNA (inclisiran) after randomization, and before the EOS visit.

Since change of dosing regimen will result in a new entry on the medication CRFs, to determine the treatment duration, entries for medications of the same class (any statin, either of the PCSK9i mAbs), or the same preferred name (non-statin oral LMT) will be combined if the gaps between entries are ≤ 7 days (for oral drugs), or ≤ 30 days (for PCSK9 mAb injections).

The date of starting first adjunctive cross-in LMT is defined to be the start date of the first medication that meets the cross-in criteria.

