8.2.2. Permitted Medications

Permitted medications must be stable for at least 2 weeks prior to Visit S1 (Week -5) with the exception of PCSK9 inhibitors, which must be stable for 12 weeks prior to screening and other lipid-regulating medications that must be stable for 4 weeks prior to screening and during the study. Stable is defined as no addition or cessation of a drug or change in the dose of a drug.

Lipid-regulating medications and dietary supplements including but not limited to:

Statins – permitted only at average daily doses defined below provided these statin/doses are currently well tolerated. However, beginning at Month 6, if the threshold for elevated LDL-C levels has been met and confirmed as described in the monitoring and management section of the protocol (Section 12.1.6.3.3), average daily doses of statins greater than those listed below may be used in accordance with the standard of care and local practice. Simvastatin at average daily doses greater than or equal to 40 mg and pravastatin at average daily doses greater than or equal to 80 mg may not be used while the patient is taking IMP.

- Atorvastatin <10 mg
- Fluvastatin <40 mg
- Lovastatin <20 mg
- Pravastatin <40 mg
- Pitavastatin <2 mg
- Rosuvastatin <5 mg
- Simvastatin <10 mg

Selective cholesterol and/or bile acid absorption inhibitors

- Cholestyramine/Colestipol/Colesevelam hydrochloride
- Ezetimibe

Fibrates

- Fenofibrate
- Bezafibrate
- Ciprofibrate
- Gemfibrozil

PCSK9 inhibitors

- Evolocumab
- Alirocumab
- Other PCSK9 inhibitors that may become commercially available

Niacin derivatives

Other TG-lowering agents containing

- Eicosapentaenoic acid (EPA) and/or
- Docosahexaenoic acid (DHA)

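### SAP 7.6.4 matches non-statin oral lipid drugs by preferred name, so an in-class switch can count as cross-in while back-to-back use of two drugs from a newly started class can be missed

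*SAP*

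**What the plan says.** SAP 7.6.4 has three criteria for cross-in lipid-modifying therapy and one rule for turning medication entries into a treatment duration.

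- **Non-statin oral drugs (criterion 2).** These count if they are drugs "that were not used at baseline (same preferred name), started after randomization and continued for 90 days or more". The list covers bile acid sequestrants, fibrates, niacin derivatives, ezetimibe, commercial bempedoic acid and the commercial bempedoic acid/ezetimibe product.
- **Statins (criterion 1).** The test is class-wide: "Any statin, regardless of the specific drug, started after randomization, with increased intensity if used at baseline, and continued for 90 days or more".
- **Duration rule.** It takes "entries for medications of the same class (any statin, either of the PCSK9i mAbs), or the same preferred name (non-statin oral LMT" as the units, and these "will be combined if the gaps between entries are ≤ 7 days (for oral drugs".
- **Start date.** "The date of starting first adjunctive cross-in LMT is defined to be the start date of the first medication that meets the cross-in criteria".

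SAP 15.4.3 uses that start date. MACE-4 and MACE-3 are censored in the PPS 30 days after it, or at the ordinary censoring date if earlier. LDL-C and hs-CRP values taken more than 7 days after it are left out of the Month 6 summaries. SAP 13.3 tabulates cross-in use and time to first cross-in.

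SAP 7.6.1 already sorts non-statin drugs into classes, using the ATC level 4 term for bile acid sequestrants, fibrates and niacin derivatives. Protocol 8.2.2 permits several drugs within a class. Its bile acid sequestrant entry reads "Cholestyramine/Colestipol/Colesevelam hydrochloride", and it names four fibrates.

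**The concern.** The SAP 15.4.3 analysis is meant to show the treatment effect without added lipid therapy that might blur the contrast between arms. For that purpose a substitution within a class is not an addition, whereas a class that is newly started and kept up is. Preferred-name matching can get both wrong.

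- **Cross-in declared with no class added.** A patient who changes from one fibrate or resin to another has a drug whose name was absent at baseline. After 90 days on it the patient is cross-in, dated to the switch, and later follow-up is discarded.
- **Cross-in missed.** A patient who starts a new class and changes drug within it before day 90 has two names. Each is timed separately and neither reaches 90 days. The patient stays in the analysis as free of cross-in.

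The same section avoids the second problem for statins and for the two PCSK9 antibodies by joining their entries by class. It gives no reason for handling oral non-statins differently. Protocol 15.9 asks for added lipid therapy to be summarised by drug class.

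**Working it through.** The plan states no figure on this point to reproduce, so the check applies the rule to test patients.

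**Inputs.** Baseline match on preferred name, minimum run of 90 days, and joining across gaps of up to 7 days for oral drugs (all SAP 7.6.4); censoring at start + 30 days (SAP 15.4.3). The drugs are from Protocol 8.2.2.

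**Formulas**, in days from randomization:
- length of a run = stop − start + 1
- gap = next start − previous stop − 1
- cross-in if the drug (or class) was absent at baseline and the length is at least 90
- censoring day = start + 30, if no event or ordinary censoring comes first

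| Baseline | After randomization | By preferred name (as written) | By SAP 7.6.1 class |
|---|---|---|---|
| Fenofibrate | Bezafibrate, days 200–900 | 900 − 200 + 1 = 701 days; cross-in day 200, censored day 230 | No cross-in |
| Cholestyramine | Colesevelam, days 200–900 | Same: cross-in day 200, censored day 230 | No cross-in |
| Fenofibrate | Bezafibrate, days 200–288 | 89 days, under 90; no cross-in | No cross-in |
| None | Fenofibrate 200–259, then bezafibrate 260–319 | Runs of 60 and 60; no cross-in | Gap 0, 60 + 60 = 120 days; cross-in day 200, censored day 230 |
| None | Fenofibrate 200–288, then bezafibrate 289–377 | Runs of 89 and 89; no cross-in | 89 + 89 = 178 days; cross-in day 200, censored day 230 |
| None | Fenofibrate, two entries, 200–259 and 260–319 | Same name, 120 days; cross-in day 200 | Same |
| Fenofibrate | Ezetimibe added, days 200–900 | Cross-in day 200 | Same |

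The first two rows show cross-in with no class added. Rows four and five show up to 178 continuous days of a new class counted as none. Row six shows that the length of exposure is not what decides: the same 120 days under one name is counted. The last row shows that class matching still catches the addition of a different class.

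**Statins for comparison.** Two different statins for 60 + 60 days without a gap would be joined into 120 days. They would count if no statin was used at baseline or if the intensity rose.

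**Search for an exemption.** Nothing in SAP 7.6, 13.3 or 15.4.3 exempts an in-class switch or adds up different non-statin oral drugs of one class.

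**The case against.** The best case for the current wording is that the protocol's unit of change is the drug. Protocol 8.2.2 treats background therapy as stable only if no drug is added or stopped and no dose is changed. Replacing one fibrate by another is both an addition and a cessation, and SAP 7.6.4 itself speaks of starting new non-statin therapy. Statins also have an intensity scale (SAP 7.6.2), so a statin switch can be tested for intensification. No such scale exists for fibrates, resins or niacin, and two drugs of one class need not be equally potent.

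Part of this stands. It makes the baseline test arguable, and it means nobody can say from the documents that a given in-class switch left lipid lowering unchanged. Two things limit it. Name matching is not a potency test either: under criterion 2 a dose increase of a baseline drug never counts, while a switch to another drug always does once it lasts 90 days. And the argument does not reach the duration rule, since a drug-level view of stability gives no reason to treat 120 continuous days of a newly started class as no cross-in.

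A reader might also infer more than the documents support:

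- **That ezetimibe is affected in the same way.** SAP 7.6.3 says "Baseline ezetimibe use is defined as the use of ezetimibe alone or in combinations that were ongoing at the time of randomization", and criterion 2 refers back to SAP 7.6.1, which groups products containing ezetimibe. Whether a change between a combination and plain ezetimibe alters the preferred name depends on coding that the documents do not show. SAP 7.6.1 identifies the bempedoic acid/ezetimibe product by verbatim term or brand name and notes that the dictionary lacks some suitable preferred names.
- **That the PCSK9 baseline test should also become class-wide.** The SAP gives no intensity ranking between alirocumab and evolocumab, and criterion 3 counts some dose increases of alirocumab. A class-wide exemption could hide a real increase.
- **That the main result is at risk.** The primary analysis in the FAS does not censor at cross-in (SAP 7.2.5 and 15.2.2).

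**Conclusion.** The point holds for bile acid sequestrants and fibrates, where the protocol permits several drugs per class. As written, an in-class switch of 90 days or more counts as cross-in, and two consecutive shorter runs in a new class do not. The duration half is the firmer of the two; the baseline half is a matter of definition on which the SAP should at least give its reason.

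The reach is narrow: the pre-cross-in sensitivity analysis of MACE-4 and MACE-3 in the PPS, the LDL-C and hs-CRP summaries in SAP 15.4.3, and the cross-in summaries in SAP 13.3. The primary FAS analysis is untouched.

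The effect on the hazard ratio in that sensitivity analysis is probably small. The documents give neither the share of patients on these drugs at baseline nor the rate of in-class switching, so any patient count would rest on assumptions from outside them. The conclusion assumes that different drugs of a class carry different preferred names and that the rule is programmed as written. This is a minor point, worth a short correction.

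**What to change.** In SAP 7.6.4:

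1. **Duration rule.** Join non-statin oral entries by class as in SAP 7.6.1 (bile acid sequestrant, fibrate, niacin derivative, ezetimibe-containing, bempedoic acid-containing) across gaps of 7 days or less.
2. **Criterion 2.** Define absence at baseline by the same class. The bempedoic acid/ezetimibe product falls into two classes, so add that a combination counts as cross-in if any of its component classes was absent at baseline. A baseline ezetimibe user who starts that product for 90 days or more is then still counted, because commercial bempedoic acid is prohibited in the study (Protocol 8.2.1) and should not be present at baseline.
3. **PCSK9 antibodies.** Leave the baseline criterion as it is.

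The cost is two changed phrases, one added sentence and a grouping variable built from classes that the SAP already defines. The downside is that an in-class switch to a more potent drug would no longer be flagged, so list in-class switches separately by treatment group. If preferred-name matching is kept in criterion 2, state the reason and still make the first change.
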